#### Safety data

AEs are considered a secondary outcome and will be analysed as per section 9.6 of the SAP. The number and percentage of women experiencing any serious adverse events (SAEs) and suspected unexpected serious adverse reactions (SUSARs) will be presented by intervention group alongside the number of events reported. Statistical significance will be determined (p-value generated) through examination of the associated chi-squared statistic. A template for reporting is given in section 9 of the supplementary analysis report.

#### Planned subgroup analyses

Interpretation of subgroup analyses will be treated with caution (output will be treated as exploratory rather than definitive [10]). Analyses will be limited to the primary outcome only, and the following subgroups:

Baseline serum hCG levels (<1500 IU/L,  $\geq$ 1500 to <2500 IU/L,  $\geq$ 2500 IU/L) BMI (<25 kg/m^2,  $\geq$ 25 kg/m^2) Ectopic size on ultrasound (<2cm,  $\geq$ 2cm)

Baseline serum hCG levels is the single key subgroup of interest (i.e. we propose to be able to draw a firm conclusion about any differential effect with respect to this variable only). We hypothesise that there will be a greater differential effect of treatment (reduction in surgical intervention with MTX and gefitinib) for those with lower baseline serum hCG levels. Other subgroup analyses will be considered exploratory. The effects of these subgroups will be examined by including a treatment group by subgroup interaction parameter in the regression model. P-values from tests for statistical heterogeneity will be presented alongside the effect estimate and 95% confidence interval within each subgroup. In addition to this, a ratio(s) (and 95% Cl(s)) will be provided to quantify the difference between the treatment effects estimated within each subgroup. For BMI and ectopic size as these subgroup variables contain only two levels, one ratio will be provided. For hCG level, which has three levels, '>2500 IU/L' will be considered as the reference group and two ratios will be provided for the other levels in comparison to this reference. Given there is only one key subgroup analyses for the primary outcome is given in section 8.1.5 of the supplementary template report.

Sensitivity or supportive analyses

Sensitivity analyses for the primary outcome only will consist of:

A per-protocol (adherent) analysis (population described in sections 5.3 and 5.4);

A sensitivity analysis which excludes any women who are found to violate the inclusion/criteria. An analysis to assess the effect of missing responses for the primary outcome only. Unadjusted models will be utilised. This analysis will explore the possibility that missing responses are 'missing not at random' (MNAR) using a tipping point approach. In this analysis, for women with missing outcome data, events will be added sequentially in each of the groups in turn to determine the point where the general conclusion changes (for example from positive to inconclusive in terms of the CI). An assessment can then be made about whether the event rate in the missing responses between groups is likely to be plausible when compared with the event rate in the non-missing data. Two scenarios will be considered as follows:

Scenario A: In the MTX and placebo group, assume all missing responses are non-events (i.e. surgical intervention is no). For missing responses in the MTX and gefitinib group, we will first replace X missing responses with events (i.e. X additional cases of surgical intervention) where X is the number of events such that the event rate in the missing responses is equal to the event rate in the non-missing responses in the MTX and gefitinib group (for example if the event rate in the non-missing data in the MTX and gefitinib group is 30% and we have 10 missing responses we will add  $0.3*10 \sim 3$  events [number of events rounded to the closest integer >0]). This will be regarded as the base case. All other missing responses in the MTX and gefitinib group will be considered as non-events. An unadjusted model will be fitted. Event rates will be compared between groups. The CI from the treatment estimate (from the RR of the log-binomial model) will be examined and stored. Following the base case, an additional event will be added to the MTX and gefitinib group and the above procedure repeated (unadjusted model fitted and the RR and CI examined). This process will end when the number of events added to the MTX and gefitinib group are equal to the original number of missing responses in this group. The tipping point for the MTX and gefitinib group will occur when enough events have been added such that the upper/lower limit of the CI from the corresponding model differs from that of the primary ITT finding (in regards to whether the CI crosses the null value of one).

Scenario B: In the MTX and gefitinib group, assume all missing responses are non-events (i.e. surgical intervention is no). For missing responses in the MTX and placebo group, we will first replace X missing responses with events (i.e. X additional cases of surgical intervention) where X is the number of events such that the event rate in the missing responses is equal to the event rate in the non-missing responses in the MTX and placebo group (for example if the event rate in the non-missing data in the MTX and placebo group is 30% and we have 10 missing responses we will add 0.3\*10 ~ 3 events [number of events rounded to the closest integer >0]). This will be regarded as the base case. All other missing responses in the MTX and placebo group will be considered as non-events. An unadjusted model will be fitted. Event rates will be compared between groups. The CI from the treatment estimate (from the RR of the log-binomial model) will be examined and stored. Following the base case, an additional event will be added to the MTX and placebo group and the above procedure repeated (unadjusted model fitted and the RR and

CI examined). This process will end when the number of events added to the MTX and placebo group are equal to the original number of missing responses in this group. The tipping point for the MTX and placebo group will occur when enough events have been added such that the upper/lower limit of the CI from the corresponding model differs from that of the primary ITT finding (in regards to whether the CI crosses the null value of one).

For both scenario A and scenario B, results will be presented visually. The event rate (surgical intervention rate) in the missing data in the MTX and gefitinib group (scenario A) or MTX and placebo group (scenario B) will be plotted on the x-axis. The RR (MTX and gefitinib vs. MTX and placebo) from the model will be on the plotted on the y-axis. The corresponding CI will be included around each RR. If the CI in the ITT analysis contains one, then the point where the upper CI falls below or above one will be highlighted (tipping point) on the plot. If the CI in the ITT analysis does not contain one (i.e. one treatment is superior to the other), then the point where the CI crosses one will be highlighted (tipping point). The base case will also be highlighted on each plot.

Sensitivity analyses for the secondary outcomes only will consist of:

A sensitivity analysis where a threshold of  $\leq$ 30 IU/L is used for time to hCG resolution (days).

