#### Sample size

The target sample size of 328 participants is based on data taken from the Phase II study (GEM2), published cohort data [1] and an audit of Edinburgh and Imperial of women undergoing usual care (2012; focusing on those participants with serum hCG >1000 IU/L). The cohort and audit data suggest a 30% rate of surgical intervention in the MTX group, with 15% expected in the MTX and gefitinib group (actual figure from the phase II study was 14% but this has been conservatively rounded up). To detect this absolute difference in proportions of 15% with 90% power and an alpha error rate of 5%, a total of 322 participants would need to be randomised (161 per group). Assuming and adjusting for a 2% loss to follow-up rate, 328 participants need to be recruited.

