#### Framework

The objective of the trial is to test the superiority of one intervention to another. The null hypothesis is that there is no difference in surgery rates between women allocated to MTX and gefitinib vs. women allocated to MTX and placebo. The alternative hypothesis is that there is a difference between the groups.

Interim analyses and stopping guidance

If gefitinib in combination with MTX is overwhelmingly better or worse than MTX alone with respect to reducing the rate of surgical intervention for resolution of EP, then this effect may become apparent before the target recruitment has been reached. Alternatively, new evidence could emerge from other sources to suggest that gefitinib in combination with MTX is definitely more, or less, effective than MTX alone. To protect against any unnecessary continuance of the

trial in this event, interim analyses of major endpoints and safety data will be supplied during the period of recruitment to the study, in strict confidence, to the Data Monitoring Committee (DMC) along with updates on results of other related studies, and any other analyses that the DMC may request.

The DMC will advise the chair of the Trial Steering Committee (TSC) if, in their view, any of the randomised comparisons in the trial have provided both: a) proof beyond reasonable doubt that for all, or for some, types of participant one particular intervention is definitely indicated or definitely contra-indicated in terms of a net difference of a major endpoint, and b) evidence that might reasonably be expected to influence the patient management of many clinicians who are already aware of the other main trial results. Unless this happens, however, the TSC, the collaborators and all of the central Trial staff (except the statisticians who supply the confidential analyses) will remain ignorant of the interim results.

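### The SAP reserves a firm conclusion for the baseline hCG subgroup, but a trial sized only for the overall effect cannot deliver one in either direction

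*SAP*

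**What the plan says.** SAP section 9.9 (Planned subgroup analyses) opens with a general caution covering subgroup analyses: "output will be treated as exploratory rather than definitive". It then lists three subgroup variables and makes baseline hCG, in three bands, the single key one, saying that "we propose to be able to draw a firm conclusion about any differential effect with respect to this variable only". The remaining subgroups are labelled exploratory. The stated hypothesis has a direction: a larger reduction in surgery at lower hCG. No size is attached to it.

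The method is a treatment-by-subgroup interaction in the regression model. "P-values from tests for statistical heterogeneity will be presented alongside the effect estimate" and its confidence interval in each band, and two ratios of treatment effects are reported against the top hCG band. Section 5.1 applies the 5% significance level to subgroup p-values, and section 5.2 makes no multiplicity correction.

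The only sample size justification is in section 4.7, for the overall comparison: "The cohort and audit data suggest a 30% rate of surgical intervention in the MTX group", "with 15% expected in the MTX and gefitinib group".

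**The concern.** A claim to reach a firm conclusion about any differential effect covers two outcomes: a significant interaction (the effect differs by hCG) and a non-significant one (it does not). Naming one subgroup in advance, with a direction, limits false positives. It does not supply the information needed for either conclusion, and section 4.7 provides none for an interaction.

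At stake is how the subgroup result may be reported. With the wording as it stands, a null test could be presented as pre-specified firm evidence of a uniform effect across hCG bands, or one significant result as firm evidence that only some bands benefit. Either could affect which women are thought to gain from the drug. The primary result is not affected.

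**Working it through.** **Inputs from the SAP.** Risks 30% and 15%, 90% power, 5% alpha and 161 per group (section 4.7); 1:1 allocation (section 4.6); a non-directional alternative, "The alternative hypothesis is that there is a difference between the groups" (section 4.8), so two-sided; three hCG bands (section 9.9).

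**Assumed, because the SAP gives neither.** Shares of women by hCG band (low/middle/high): equal thirds, 50/25/25 and 25/25/50, with 40/30/30 and 60/20/20 added for the Wald formula. Placebo risk: 30% in every band, or 20/30/40% rising with hCG.

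**The plan's own figure.** With the pooled variance under the null and no continuity correction,
n = [1.96 × √(2 × 0.225 × 0.775) + 1.2816 × √(0.30 × 0.70 + 0.15 × 0.85)]² / 0.15² = 160.8, so 161 per group and 322 in all. 322/0.98 = 328.6, consistent with 328. The figure reproduces. Expected events: 161 × 0.30 + 161 × 0.15 = 48.3 + 24.2 ≈ 72, or about 24 per band with equal thirds.

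**Formula for the interaction.** For band k with n women per arm, the variance of the log RR is v = (1−pC)/(n·pC) + (1−pT)/(n·pT). With weights w = 1/v and weighted mean log RR m, the noncentrality is λ = Σ w(log RR − m)². Power is the probability that a noncentral chi-square with 2 df exceeds 5.99.

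**Worked example: 2-fold, RRs 0.35/0.50/0.70, equal thirds, 30% placebo risk.** n = 161/3 = 53.7 per arm per band. The variances are 0.202, 0.149 and 0.114, m = −0.634 and λ = 1.56, so power is 18%.

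**Worked example: 4-fold, RRs 0.25/0.50/1.00, same setting.** The variances are 0.273, 0.149 and 0.087, m = −0.445 and λ = 5.93, so power is 58%.

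**Range over the assumptions.** The likelihood-ratio column is from simulation, 3,000 runs per scenario. That test rejected 5.5–6.1% of the time when effects were equal, so its power figures are slightly flattering.

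| RRs (low/mid/high hCG) | High-to-low ratio | 2-df Wald | 2-df likelihood ratio |
|---|---|---|---|
| 0.40/0.50/0.60 | 1.5-fold | 8–10% | 9–11% |
| 0.35/0.50/0.70 | 2-fold | 16–20% | 18–21% |
| 0.25/0.50/0.75 | 3-fold | 26–39% | 32–39% |
| 0.25/0.50/1.00 | 4-fold | 48–62% | 56–67% |
| 0.125/0.50/1.00 | 8-fold | 55–81% | 74–89% |

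By the Wald formula, 80% power needs a 5.5- to 8-fold difference. With equal thirds and 30% placebo risk, 80% power needs about 1,995 women for the 2-fold pattern and about 523 for the 4-fold pattern.

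**What a null result could exclude.** If the RR is 0.5 in every band (equal thirds, 30% placebo risk), v = 0.149 in each. The SE of the lowest-to-highest log ratio is √(0.149 + 0.149) = 0.546, and the expected 95% CI is exp(±1.96 × 0.546) = 0.34 to 2.92. With shares 25/25/50 and placebo risks 20/30/40% it widens to 0.29 to 3.41.

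**What a positive result would mean.** In the 2-fold example the SE of that log ratio is √(0.202 + 0.114) = 0.562, and exp(1.96 × 0.562) = 3.0. For its CI to exclude one, the estimated ratio would have to be about 3-fold or more, which overstates a true 2-fold difference.

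**A test matched to the direction.** A 1-df linear trend over the three bands (equal thirds, 30% placebo risk) gives 11% against 9% for the 1.5-fold pattern, 24% against 18% for 2-fold, 41% against 32% for RRs 0.30/0.50/0.80, and 68% against 58% for 4-fold.

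**The case against.** - **The section may not contradict itself.** It labels the remaining subgroups exploratory, so hCG can be read as a deliberate exception to the opening caution. This stands: a reader might infer a flat contradiction, but the text supports only an exception that is not spelled out. The exception still rests on a claim of firmness that the design cannot support.
- **Power depends on assumptions.** This is true, since the SAP gives no hCG shares or band risks. A reader might also infer that power is near 10% even for large interactions. The figures do not show that: values near 10% belong to a modest 1.5-fold pattern, and an 8-fold pattern could reach 89%. For 2- and 4-fold differences the ranges are stable enough to carry the point.
- **Safeguards exist.** Section 9.9 asks for caution, band-specific estimates and ratios with CIs, and nothing in it says a null test will be read as equal effects. This also stands. The concern is what the wording permits, not a stated intention. Wide CIs would show the imprecision, which is why a promise of firmness should not stand beside them.
- **The heterogeneity test is a standard choice.** This stands too. A trend test gains little and makes none of these patterns adequately powered. Nor do the documents support requiring continuous log hCG: the amendment table records a reasoned move to categorised hCG because of skew, and no power was computed for a log hCG term.
- **One sentence near the end of section 9.9 reads as if text were lost.** It may have qualified the hCG analysis. No weight is placed on what it omits.

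**Conclusion.** The claim of a firm conclusion on hCG is not supported by the planned design. At 322 evaluable women the three-level interaction test would miss a 2-fold difference in RR about four times in five. It would miss a 4-fold difference, with no effect at all in the top band, between about one-third and one-half of the time. A truly uniform effect would still leave roughly 3-fold differences in either direction unexcluded.

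These figures rest on assumed hCG shares and band risks and on unadjusted calculations. Covariate adjustment and the random centre intercept would not change the order of magnitude. The defect is one of wording and interpretation. The choice of a 2-df test is a secondary matter, not an error.

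**What to change.** In section 9.9:

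1. Delete the statement that a firm conclusion can be drawn for hCG. Describe hCG as the single pre-specified key subgroup, interpreted as exploratory like the others, so that it agrees with the opening sentence.
2. State that the trial is not powered for interaction, that a non-significant test is not evidence of equal effects across hCG bands, and that interpretation rests on the ratios of RRs and their CIs.
3. Optionally, because the hypothesis is directional, base the hCG interaction test on a 1-df term using an ordered score for the existing three categories. Keep the band-specific RRs and the two ratios for display. This gains about 2–10 percentage points of power and keeps the categorised form adopted in version 2.0. The price is less power against a non-monotone pattern, which the SAP does not hypothesise.

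Items 1 and 2 cost a few sentences. Item 3 costs one model term. None needs new data or changes the primary analysis.

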#### Covariate adjustment

In the first instance, intervention effects between groups for all outcomes will be adjusted for the minimisation parameters listed in section 4.6. Centre will be included with a random intercept in the model, and all other factors as fixed effects (with the exception of time to event outcomes where centre will be regarded as a fixed effect).

If covariate adjustment is not possible (e.g. the model does not converge), randomising centre will be removed first. If this reduced model still fails to converge, unadjusted estimates will be produced and it will be made clear in the final report why this occurred (e.g. not possible due to low event rate/lack of model convergence).

For binary outcomes only, if the (full) adjusted log-binomial model fails to converge (when estimating a risk ratio); a Poisson regression model with robust standard errors will be used to estimate the same parameters [6]. If this also fails to converge, estimates will be produced from the log-binomial model (following rules for removal of variables as outlined above). It will be made clear in the final report why this occurred (e.g. not possible due to low event rate/lack of model convergence).

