#### Handling missing data

In the first instance, analysis will be completed on received data only with every effort made to follow-up participants even after protocol violation to minimise any potential for bias. To examine the possible impact of missing data on the results, and to make sure we are complying with the ITT principle, sensitivity analyses will be performed on the primary outcome measure (surgical intervention) [7]. See section 9.10 for further details.

Data manipulations

See Appendix D.

Analysis methods – primary outcome

A template for reporting the primary outcome is given in section 8.1 of the supplementary analysis report. The primary outcome will be summarised using frequencies and percentages. A mixed effects log-binomial model will be used to generate an adjusted risk ratios (RR) (and 95% CIs). Adjusted risk differences (RD) (and 95% CIs) will also be presented (using an identity link function). Statistical significance of the treatment group parameter will be determined (p-value generated) through examination of the associated chi-squared statistic (this will be obtained from the model which produces the RR). See section 9.1 for covariate adjustment and model convergence.

Analysis methods – secondary outcomes

A template for reporting the secondary outcomes is given in section 8.2 of the supplementary analysis report. See section 9.1 for covariate adjustment and model convergence.

Time to hCG resolution will be considered in a competing risk framework [8]. This is to account for participants who have surgical intervention for their EP, which interferes with the natural path of hCG levels and hence hCG resolution (≤15 IU/L). A cumulative incidence function will be used to estimate the probability of occurrence (hCG resolution) over time. This method is favoured over Kaplan-Meier methods which may overestimate this probability. A Fine-Gray model will be used to estimate subdistribution adjusted hazard ratios (and 95% CIs) directly from the cumulative incidence function. In addition, a further Cox Proportional Hazard model will be fitted and applied to the cause-specific (non-surgical resolution) hazard function and used to generate

adjusted hazard ratios (and 95% CIs) (effectively censoring surgical events at the point of surgery) [9].

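### The tipping-point rule sets unadjusted CIs against the adjusted ITT CI, so in a borderline trial a change of model can be reported as an effect of missing responses

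*SAP*

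**What the plan says.** Section 9.5 defines the primary result: "A mixed effects log-binomial model will be used to generate an adjusted risk ratios (RR) (and 95% CIs". It is fitted to received data (section 9.3). Section 9.1 supplies the covariates: "intervention effects between groups for all outcomes will be adjusted for the minimisation parameters listed in section 4.6", that is hCG category, BMI, ectopic size and centre, with centre as a random intercept. An unadjusted primary estimate appears only at the end of the convergence rules: "If this reduced model still fails to converge, unadjusted estimates will be produced".

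Section 9.10 specifies the missing-data analysis differently: "Unadjusted models will be utilised". At each step, "The CI from the treatment estimate (from the RR of the log-binomial model) will be examined and stored". In scenario A the tip is reached when "the upper/lower limit of the CI from the corresponding model differs from that of the primary ITT finding", judged by whether the CI crosses one. Scenario B applies the same rule to the other arm: "The tipping point for the MTX and placebo group will occur when enough events have been added". Each plot highlights the base case and the tip.

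**The concern.** A tipping-point analysis should vary one thing, the outcomes assumed for women with missing responses. Here the steps and their reference also differ in the model. Minimisation balances the arms on the adjustment factors. Where those factors predict surgery, the unadjusted estimate stays about the same but its standard error is larger. If the adjusted CI only just excludes one, the unadjusted CI from the same observed women may include it. The rule would then show a tip at the base case, and the reader would put it down to missing responses.

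The SAP plans no unadjusted fit to the received data that would expose this. The base case cannot serve: it has already filled in both arms, and the rule refers to the ITT finding, not to the base case. The planned loss is 2%, about six women (328 − 322), or three per arm. Each scenario therefore has very few steps, and the first one carries much of the message.

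**Working it through.** **1. The plan's own figure.** Section 4.7 gives 30% versus 15%, 90% power and 5% alpha, taken as two-sided in line with the CIs of section 5.1. The pooled-variance formula without continuity correction gives 161 per arm, 322 in total, with power 0.900. This agrees with the SAP. It sets the scale but does not decide the point.

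**2. How close the crossing is.** For unadjusted counts, SE(log RR) = √(1/a − 1/n + 1/b − 1/m), with a/n gefitinib and b/m placebo.
- 32/161 versus 48/161: RR 0.667, upper limit 0.985.
- 33/161 versus 48/161: RR 0.688, SE 0.1968, z = 0.3747/0.1968 = 1.904, upper limit 1.011.

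One event decides the crossing.

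**3. The mechanism on the same women.** Take 33/161 versus 48/161 and assume that adjustment leaves the RR unchanged and makes the SE 4% smaller, the strong end of the simulated range. The SE is 0.96 × 0.1968 = 0.1889, z is 1.984, and the upper limit is exp(−0.3747 + 1.96 × 0.1889) = 0.996. The adjusted CI excludes one and the unadjusted CI does not, with nothing filled in. If adjustment makes the SE only 1% smaller, the upper limit is 1.007 and the models agree.

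**4. Frequency before anything is filled in.** Two simulations used robust Poisson regression (the SAP's first fallback) with and without the minimisation factors, and without centre.
- First: 322 women, 1,500 trials per setting. Assumed hCG range 1000 to 5000 IU/L, RR per hCG doubling about 1.15 to 1.6, ectopic size RR 1.3, BMI RR 1.1. The adjusted SE was 1 to 4% smaller. The CIs disagreed in 0.20 to 1.13% of trials at a true RR of 0.5 and in 1.20 to 2.60% at 0.65. Where the adjusted p was 0.02 to 0.05, the unadjusted CI included one in 2.4 to 16.0% and 7.5 to 17.8% respectively.
- Second: 322 women, 3,000 trials per setting. Assumed hCG category shares 40/25/35%, RR for top versus bottom hCG category 1 to 4, size RR 1 to 1.5, no BMI effect. Only the adjusted CI excluded one in 0.3 to 1.9% of trials at 15% versus 30%, and in 0.5 to 6.0% at 20% versus 30%. The reverse occurred in at most 0.03%.

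**5. Frequency at the scenario A base case.** Second simulation with 328 women and three missing per arm. The first two result columns are among trials whose adjusted ITT CI excludes one; the last is among trials whose unadjusted received-data CI excludes one.

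| Rates | hCG RR, size RR | Tipped as written | Adjusted on both sides | Unadjusted on both sides |
|---|---|---|---|---|
| 15% v 30% | 1, 1 | 2.9% | 2.8% | 2.6% |
| 15% v 30% | 2, 1.2 | 4.3% | 3.7% | 3.7% |
| 15% v 30% | 3, 1.5 | 5.2% | 3.1% | 3.6% |
| 15% v 30% | 4, 1.5 | 5.2% | 2.5% | 3.4% |
| 20% v 30% | 1, 1 | 10.4% | 10.1% | 9.8% |
| 20% v 30% | 2, 1.2 | 12.7% | 9.6% | 9.9% |
| 20% v 30% | 3, 1.5 | 15.7% | 9.1% | 10.3% |
| 20% v 30% | 4, 1.5 | 19.1% | 10.3% | 10.2% |

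Row by row, the excess over the adjusted-on-both-sides column runs from 0.1 to 2.7 percentage points at the planned rates (5.2 − 2.5 in the last such row). At 20% versus 30% it reaches 8.8 points (19.1 − 10.3). With one model on both sides, the tip rate no longer climbs steadily with covariate strength.

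**The case against.** The strongest defence is that unadjusted steps are a coherent choice. Section 9.10 adds a number of events without saying which women receive them. An unadjusted RR needs only counts, whereas an adjusted RR depends on the hCG category and centre of the woman given each event. Section 5.5 also treats women who withdraw consent for use of their data as missing responses, and the SAP does not show that their covariates could be used. This stands: the fault lies in the reference, not in the unadjusted steps.

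The output is also more than a verdict. Every RR and CI is plotted, the base case is marked, and plausibility is then judged. A tip at the base case would be seen, but its cause would not be isolated.

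Three stronger readings do not hold.
- A reader might infer that the robustness statement will be wrong in borderline trials. With an adjusted p of 0.02 to 0.05 the two CIs still agree in about 82 to 98% of simulated trials. Nor is every disagreement a misreported tip. In the example of step 3, with three missing per arm, the scenario A base case is 34/164 versus 48/164. Its upper limit is 1.038 unadjusted and 1.022 with the SE 4% smaller, so either model crosses one.
- A reader might infer that a tip would be reported even with nobody missing. Without missing responses the procedure has no base case and no steps.
- A reader might infer that adjusted refits are the obvious remedy. They need an assignment rule, and the convergence rules of section 9.1, applied afresh at each step, could change the model between steps and bring the same problem back.

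**Conclusion.** The point holds as a limited one. The mismatch is explicit in the text and applies to both scenarios. Following the rule exactly can report the removal of covariates as an effect of missing responses. The error runs almost wholly one way: a significant result looks more fragile than it is, so it gives no false reassurance about a positive finding.

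At the planned effect it is small: about 0.2 to 2% of trials disagree before any filling in, and most base-case tips come from the filled-in responses themselves. It matters for a borderline result with prognostic minimisation factors. All these sizes rest on covariate strengths that the SAP does not give, on robust Poisson in place of the mixed log-binomial model, and on leaving centre out. The 20% versus 30% figures also assume a smaller effect than planned. The primary estimate, CI and p-value are untouched. If the primary model falls back to unadjusted estimates, the mismatch disappears.

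**What to change.** In section 9.10, fit the unadjusted log-binomial model to the received data and show its RR and CI as step 0 on both plots. Define the tip in scenarios A and B against that CI instead of the adjusted ITT CI. Report whether step 0 agrees with the adjusted ITT finding on crossing one; if it does not, say that the difference comes from the model and not from missing responses.

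The cost is about one sentence, one extra fit, and a reference that is not the headline estimate. Refitting the adjusted model at each step is an alternative only if the SAP also fixes which missing women receive the added events and keeps a single model across all steps.

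### Each tipping-point scenario fixes one arm's missing women as having no surgery, so its base case is already unequal between arms and can change a borderline conclusion

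*SAP*

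**What the plan says.** SAP section 9.3 makes analysis of received data primary and refers to section 9.10 for sensitivity to missing data. Section 9.10 gives one such analysis for surgical intervention, a tipping-point analysis with unadjusted log-binomial models and two scenarios.

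- **Scenario A.** "Scenario A: In the MTX and placebo group, assume all missing responses are non-events (i.e. surgical intervention is no". Missing gefitinib women first receive enough events to match the observed gefitinib rate, with the "number of events rounded to the closest integer >0". This is named the base case. Gefitinib events are then added one at a time until all missing women in that arm are events.
- **Scenario B.** The mirror image: "In the MTX and gefitinib group, assume all missing responses are non-events (i.e. surgical intervention is no". The placebo arm starts at its observed rate and has events added.

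The tipping point is where the interval for the risk ratio (RR) differs from the intention-to-treat finding on whether it includes one. The plot has the varied arm's missing-data event rate on the x-axis and highlights the base case. The stated purpose is a plausibility judgement: "An assessment can then be made about whether the event rate in the missing responses between groups is likely to be plausible", by comparison with the observed data.

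**The concern.** A reader takes a base case as the reference point from which departures are measured. Here it combines an observed rate in one arm with 0% in the other. In Scenario A the arm held at 0% is placebo, where the SAP expects 30% surgery (section 4.7). The starting point therefore already departs from the observed data, in a known direction, and no later step relaxes the 0%. The x-axis does not show it either.

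Two things are at stake. A conclusion can change at the base case itself, before any event beyond it is added, and this may be read as a lack of robustness even if missing women resemble observed women. And the count of extra surgeries needed to overturn a positive result is understated in Scenario A, because the placebo arm is never given its own share of events.

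**Working it through.** **Inputs from the SAP.** Section 4.7: "The cohort and audit data suggest a 30% rate of surgical intervention in the MTX group", "with 15% expected in the MTX and gefitinib group"; 90% power, 5% alpha, 161 per group, 2% loss, 328 recruited. Section 4.6: 1:1 allocation. Section 5.1: two-sided 95% intervals.

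**Assumed, to show a range.** 8 or 16 missing per arm (about 5% and 10% of 164), and a true gefitinib rate of 20%. The SAP states only the 2% loss.

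**Step 1: the SAP's own figure.** With pooled variance, n = [1.960·√(2·0.225·0.775) + 1.282·√(0.30·0.70 + 0.15·0.85)]² / 0.15² = (1.157 + 0.745)² / 0.0225 = 160.8, so 161 per group and 322 in all, as stated. 322/0.98 = 328.6, consistent with 328. That is 164 per arm, with 164 − 161 = 3 missing.

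**Step 2: interval formula.** For a/n (gefitinib) v b/m (placebo), RR = (a/n)/(b/m), SE(log RR) = √(1/a − 1/n + 1/b − 1/m), limits RR·exp(±1.96·SE). This is the interval from an unadjusted log-binomial model.

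**Step 3: planned rates, 3 missing per arm.** Observed 24 v 48 of 161: RR 0.500 (0.322 to 0.775). Base case A, 25 v 48 of 164: 0.521 (0.338 to 0.802). All three missing gefitinib women as events, 27 v 48 of 164: 0.563 (0.370 to 0.855). Nothing tips.

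The observed gefitinib rate implies 3 × 24/161 = 0.45 events, which the rounding rule lifts to 1. If 0 were allowed, the cell with both arms at observed rates would be 24 v 49 of 164, RR 0.490 (0.316 to 0.759). With numbers this small it coincides with base case B, but only through rounding.

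**Step 4: borderline results.** For the first row, base case A is 33 v 48 of 164: RR 0.6875, SE 0.1973, upper limit 0.6875·exp(1.96·0.1973) = 1.012. Upper limits:

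| Missing per arm | Observed events | Observed data | Scenario base case | Both arms at observed rates |
|---|---|---|---|---|
| 3 | 32 v 48 of 161 | 0.985 | A: 1.012 (33 v 48) | 0.989 (33 v 49) |
| 8 | 30 v 47 of 156 | 0.953 | A: 1.009 (32 v 47) | 0.964 (32 v 49) |
| 16 | 27 v 44 of 148 | 0.935 | A: 1.028 (30 v 44) | 0.913 (30 v 49) |
| 3 | 33 v 48 of 161 | 1.011 | B: 0.989 (33 v 49) | 1.015 (34 v 49) |

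The last two columns use 164 per arm. In the 16-missing row, Scenario A tips at its base case of 3 events among 16. With the 16 missing placebo women given 5 events (16 × 44/148 = 4.8), tipping takes 7 of 16 (34 v 49, upper limit 1.015).

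**Step 5: how often.** All binomial outcomes were enumerated with 164 per arm. Among results whose observed-data upper limit is below 1, the share already tipped at base case A is:

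| True rates, placebo v gefitinib | 3 missing | 8 missing | 16 missing |
|---|---|---|---|
| 30% v 15% | 3.2% | 4.4% | 12.6% |
| 30% v 20% (assumed) | 10.7% | 18.3% | 36.2% |

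With both arms at their observed rates the share is 0% to 1.7% throughout. As a share of all trials rather than of significant ones, the 16-missing figures are 11.0% and 18.3%.

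**The case against.** The analysis is declared to explore data missing not at random, so unequal assumptions are its purpose. The SAP states the fixed 0% at the start of each scenario, requires event rates to be compared between groups, and asks for a plausibility judgement. All of that is true. It does not supply a reference step with both arms at their observed rates, nor a run that relaxes the 0%.

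The example at 2% loss sits on the significance boundary: with no missing data, 33 v 48 of 161 already gives 1.011 and 32 v 47 gives 1.008. Such a result is fragile in any case, and this stands for 3 missing per arm. It does not carry over to 16 missing, where 27 v 44 of 148 stays significant with one or two more gefitinib events (0.964, 0.993) yet tips at the base case.

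The received-data analysis already comes close to the both-observed-rates case (0.985 against 0.989). This largely stands, but that model is adjusted while the tipping models are not, so the match is approximate and the reference point is absent from the plot.

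Missing outcomes may also be few: under Appendix D, a woman not followed to hCG resolution still counts as having no surgery if the site confirms it. This limits the likely size.

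Four stronger readings are not supported:

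- The SAP does not call its base case neutral.
- The base case is not free of added events; it adds at least one in the varied arm.
- Scenario B is not an empty test. It cannot tip a beneficial result, but it does test an inconclusive one, as the last row of the first table shows.
- The rule that at least one event be added is not a material flaw. It shifts the base case by at most one event: allowing 0 changes the 3-missing shares from 3.2% to 2.1% and from 10.7% to 10.2%, and leaves the others unchanged.

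**Conclusion.** The point holds as a design weakness in a supportive analysis. Each base case is a differential missing-not-at-random assumption, and neither scenario specifies a step with both arms at their own observed rates. A borderline conclusion can change at the base case in either direction.

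At the planned 30% v 15% with 2% loss the expected result does not change at any step of Scenario A, and Scenario B only moves it further from one. The effect grows with borderline results or with more missing data than planned. The 13% figure assumes 16 missing per arm, about five times the planned number; the 36% figure also assumes a 20% gefitinib rate that the SAP does not state. Neither is a forecast. All figures use unadjusted intervals. A reader might infer that the primary result is at risk; it is not, since the primary estimate and p-value do not depend on this analysis. The change is still worth making, because this is the only missing-data sensitivity analysis of the primary outcome.

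**What to change.** In section 9.10, replace the two one-way runs with a two-way grid. For every number of events from 0 to all among the missing gefitinib women, crossed with the same for the missing placebo women, fit the unadjusted model and record whether the interval includes one. Mark as base case the cell with both arms at their own observed rates, rounded to the nearest integer with 0 allowed. Keep Scenarios A and B as labelled edges of the grid (placebo missing events at 0, and gefitinib missing events at 0), and show both arms' missing-data rates on the plot.

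The cost is SAP wording, one nested loop and a slightly longer report: 4 × 4 = 16 cells with 3 missing per arm, 17 × 17 = 289 with 16. No new data are needed, and everything now planned in A and B is retained.
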